## 5.7.1. Analysis of Primary Efficacy Variables

For the two primary efficacy variables, the primary analyses will be conducted in Cohort A (screening baseline leptin <8.0) for the following patient subgroups:

- Fasting serum TG percent change from baseline to week 12: patients with screening fasting TG >200 mg/dL
- HbA1c absolute change from baseline to week 12: patients with screening HbA1c >7.0%

# 5.7.1.1. Percent Change in Fasting TG from Baseline to Week 12

Percent change from baseline to week 12 in fasting serum TG, will be analyzed in the FAS population for the Cohort A patients with elevated baseline fasting TG >200 mg/dL by using a mixed-effect model with repeated measures (MMRM) approach. The MMRM model will include the following effects: fixed categorical treatment groups (Placebo versus mibavademab), time points (weeks 2, 4, 6, 8, 10, 11, and 12), actual strata (screening HbA1c ≤7.0%, >7.0%), strata-by-time-point interaction, and treatment-group-by-time-point interaction, as well as the continuous fixed covariates of baseline TG value and baseline value-by-time point interaction. Logarithm transformation will be performed to normalize the fasting TG.

Regeneron Pharmaceuticals, Inc.

Page 34 of 88

Protocol: R4461-PLD-20100

Post-baseline data available up to and including the week 12 efficacy analysis window for fasting TG (Table 11 in Appendix 10.2) will be used and missing data are accounted for by the MMRM. Measurements on not-fasting patients will be excluded. Contrast and estimate statements will be used to assess baseline adjusted least-squares (LS) means estimates at week 12 for each treatment group with their corresponding 95% confidence intervals. The LS means at week 12 will be back-transformed into the geometric means to ease clinical interpretation of the result. The difference between the two study treatment groups (mibavademab, placebo) in geometric means will be provided along with its corresponding 95% confidence interval, and nominal p-value.

To support interpretation of the TG results at week 12, descriptive summaries will be provided at each protocol specified DBTP visit. Median percent changes (with Q1 and Q3 bars) will be plotted across visits by treatment group. A spaghetti plot will be provided for individual patient data across visits by treatment group.

## **Sensitivity Analysis**

- A non-parametric approach will be performed on the primary efficacy endpoint for comparing the mibavademab and placebo. Specifically, the percent change in fasting serum TG from baseline to week 12 will be ranked for an analysis of covariance (ranked ANCOVA). For the case >5% missing data at week 12, missing data will be imputed using multiple imputation based on other observed measurements. The ranked ANCOVA model will be able to provide significance of the treatment effect as compared to placebo. Nominal p-values will be provided as a measure of the strength of evidence. Median treatment difference and its 95% confidence interval can be derived from the Hodges-Lehmann estimation and Moses distribution free confidence interval respectively.
- To assess the impact of a systemic dosing error on the primary efficacy endpoint, the primary efficacy analysis will be performed excluding affected patients. Patients known to be under dosed at the time of database lock will be identified for this analysis before database lock. Any additional patients determined to be affected post-database lock will be separately identified.

## 5.7.1.2. Change in HbA1c from Baseline to Week 12

Absolute change from baseline to week 12 in HbA1c, will be analyzed in the FAS population for the Cohort A patients using a mixed-effect model with repeated measures (MMRM) approach. The MMRM model will include the following effects: fixed categorical treatment groups (Placebo, mibavademab), time points (weeks 4, 6, 10, and 12), actual strata (screening HbA1c ≤7.0%, >7.0%), strata-by-time-point interaction, and treatment-group-by-time-point interaction, as well as the continuous fixed covariates of baseline HbA1c value and baseline value-by-time point interaction. An unstructured covariance matrix will be used to model the within patient errors. In the case that the unstructured covariance matrix does not converge, then a structured covariance matrix such as autoregressive heterogeneous [ARH] will be assessed.

Post-baseline data available up to and including the week 12 efficacy analysis window for HbA1c (Table 12 in Appendix 10.2) will be used and missing data are accounted for by the MMRM. Contrast and estimate statements will be used to assess baseline adjusted least-squares

Regeneron Pharmaceuticals, Inc.

Page 35 of 88

Protocol: R4461-PLD-20100

(LS) means estimates at week 12 in the actual strata of screening HbA1c>7.0% for each treatment subgroup with their corresponding standard errors and 95% confidence intervals. The difference of the study treatment HbA1c mean changes from baseline to week 12 for patients with screening HbA1c>7.0% will be provided along with its corresponding 95% confidence interval, and nominal p-value.

To support interpretation of the HbA1c results at week 12, descriptive summaries will be provided at each protocol specified DBTP visit. Mean changes (±SE) will be plotted across visits by treatment group. A spaghetti plot will be provided for individual patient data across visits by treatment group.

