3.2.3. Rationale for Analysis

The primary analyses are between-group comparisons (change in REGN4461 arm between baseline and week 12 versus change in placebo arm between baseline and week 12). The HbA1c and TG endpoints will be analyzed only in those individuals with corresponding pre-specified elevated baseline values. This will maximize our ability to determine treatment effects in a small study with heterogeneous baseline characteristics and inclusion criteria (Section 7.2.1).

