4. ENDPOINTS

4.1. Primary Endpoints

The co-primary endpoints are:

- Percent change in fasting serum TG from baseline to week 12 in patients with elevated baseline fasting TG (>200 mg/dL) and with baseline leptin <8.0 ng/mL (cohort A)
- Absolute change in HbA1c from baseline to week 12 in patients with elevated baseline HbA1c (>7.0%) and with baseline leptin <8.0 ng/mL (cohort A)

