#### 10. APPENDIX

### 10.1. Summary of Statistical Analyses

#### **Primary Efficacy Analysis:**

Endpoint	Analysis Populations	Statistical Method	Supportive Analysis	Subgroup Analysis	Other Analyses
Primary Endpoint					
• Change in HbA1c from baseline to week 12 in patients with elevated baseline HbA1c (ie, screening HbA1C > 7%).	Glycemic Analysis Set – Cohort A	MMRM		No	
• Percent change in fasting triglyceride (TG) from baseline to week 12 in patients with elevated screening baseline fasting TG (ie, fasting TG ≥ 200 mg/dL).	Triglyceride Analysis Set – Cohort A	MMRM	Ranked ANCOVA	No	

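### SAP 5.7.1.2 fits the HbA1c co-primary in all of Cohort A: its >7.0% difference is the common cohort effect, and the between-arm week-12 HbA1c summaries do not carry the >7.0% limit

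*SAP*

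**What the plan says.** **Where the >7.0% limit is stated.** Protocol 3.2.3 says: "The HbA1c and TG endpoints will be analyzed only in those individuals with corresponding pre-specified elevated baseline values". Protocol 4.1 and 11.4.3.1 repeat the limit for HbA1c. SAP 5.7.1 lists the primary subgroup as "HbA1c absolute change from baseline to week 12: patients with screening HbA1c >7.0" (percent), within Cohort A. The summary table in SAP 10.1 has the same threshold. The first bullet of SAP 1.2.4 moves the subgroup from baseline to screening HbA1c, which is a declared change and not part of this point.

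**Where it is not.** Under SAP 5.7.1.2 the HbA1c change "will be analyzed in the FAS population for the Cohort A patients using a mixed-effect model with repeated measures (MMRM) approach". The model includes the screening HbA1c stratum at both levels, with "strata-by-time-point interaction, and treatment-group-by-time-point interaction, as well as the continuous fixed covariates of baseline HbA1c value" and its interaction with time. Least-squares means are then taken at the >7.0% stratum, and "The difference of the study treatment HbA1c mean changes from baseline to week 12 for patients with screening HbA1c>7.0% will be provided".

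**Descriptive output.** The same section continues: "To support interpretation of the HbA1c results at week 12, descriptive summaries will be provided at each protocol specified DBTP visit". That sentence and the plots that follow it name no HbA1c subgroup.

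**Early termination.** A later bullet of SAP 1.2.4 restricts efficacy output to descriptive summaries and plots by treatment group. It names no HbA1c subgroup either. SAP 1.2.4 also drops the first-step analysis, which is where SAP 5.7 places the primary models.

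**The concern.** Two things do not fit together.

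First, 5.7.1.2 gives the co-primary analysis a wider population than the section that introduces it and wider than the protocol. Patients at ≤7.0% are a planned part of Cohort A. Protocol 3.2.1 admits them with TG >450 mg/dL, and SAP 2.2 expects 78% of patients, not all, above 7.0%.

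Second, the reported difference carries a >7.0% label that the model cannot support. Treatment enters only as a main effect and by time, so the fitted week-12 difference is the same in both strata. Evaluating it at the >7.0% stratum changes the arm-level means but not the difference between arms. SAP 5.7.2.1 and Table 3 carry a similar model to Cohort B and to Cohorts A plus B.

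If the model were run, the label would be wrong and the interval would reflect more patients than the group it names. As the SAP stands, the stake is smaller. The between-arm week-12 HbA1c summary becomes the co-primary evidence, and 5.7.1.2 places it under a whole-Cohort-A population without the limit.

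**Working it through.** **1. The plan's own precision figures.** Inputs from SAP 2.2 and Table 2: SD 1.81, 1:1 allocation, two-sided 90% interval. Half-width = t(0.95, 2n-2) × SD × √(2/n).

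| n per arm | Computed | SAP Table 2 |
|---|---|---|
| 7 | 1.724 | 1.72 |
| 8 | 1.594 | 1.59 |
| 10 | 1.404 | 1.4 |

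The table reproduces. Its 7 and 8 rows are the >7.0% subset (0.78 × 10 = 7.8 per arm) and its 10 row is all of Cohort A. The sample-size section therefore already treats the subset as the smaller analysis population.

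**2. What the >7.0% contrast estimates.** At week 12, in stratum s, the model reads: mean = intercept + treatment effect + stratum effect(s) + slope × baseline. The active-minus-placebo difference at fixed s and baseline is the treatment effect alone, and s cancels. The stated fixed effects were also fitted to 400 simulated Cohort A data sets (16 patients >7.0%, 4 at ≤7.0%). The largest gap between the two strata in the week-12 difference was 2 × 10⁻¹⁵.

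**3. Size of a possible shift.** The planned between-group effect is -0.98 (SAP Table 2 footnote), taken here as the effect at >7.0%. The documents give none at ≤7.0%, so let it be r × (-0.98) with r = 1, 0.5 or 0 (assumption). With arms balanced within strata and a share w above 7.0%:

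common effect = w × (-0.98) + (1 - w) × r × (-0.98)

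| w | r = 1 | r = 0.5 | r = 0 |
|---|---|---|---|
| 0.70 | -0.98 | -0.83 | -0.69 |
| 0.78 | -0.98 | -0.87 | -0.76 |
| 0.80 | -0.98 | -0.88 | -0.78 |

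In the simulation, with r = 0 and w = 0.80, the contrast averaged -0.83 (-0.99 when fitted only at >7.0%). The simulation error is 0.80/√400 = 0.04, so -0.83 is about one such error from -0.78.

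**4. Shift against noise.** The subset standard error is 1.81 × √(2/n): 0.91 for n = 8 and 0.97 for n = 7. At w = 0.78 the largest shift is 0.98 - 0.76 = 0.22, and 0.22/0.91 = 0.24.

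**5. Effect on an unrestricted descriptive table.** The Table 2 footnote implies a placebo change of -1.18 - (-0.98) = -0.20. Assuming that in both strata, the active-arm mean at w = 0.78 would read -1.18, -1.07 or -0.96 for r = 1, 0.5 or 0.

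**6. Precision of each model** (week 12, 10 per arm, SD 1.81, no baseline covariate):
- As in 5.7.1.2 (treatment plus stratum, 17 df): 90% half-width 1.41.
- With treatment-by-stratum added (16 df): 1.58 for an 8/2 split and 1.69 for 7/3. The expected >7.0% contrast is then -0.98 for every r.
- Restricted to >7.0%: 1.59 (8 per arm) and 1.72 (7 per arm).

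**The case against.** **The population is already settled.** SAP 1.2.4 says the SAP follows the protocol apart from listed exceptions, and widening the HbA1c population is not listed. SAP 5.7.1 sets screening HbA1c >7.0% for the primary analyses and 10.1 repeats it. The descriptive sentence comes straight after results stated for that group. This largely stands: a careful programmer could build the right table. It does not remove the conflict, because 5.7.1.2 names a different population. A model limited to >7.0% would make the stratum terms constant, and a contrast taken at one stratum presupposes both. The parallel TG model in 5.7.1.1 does state its subgroup. Table 3 separates a patient subgroup (liver fat) from a stratum level (HbA1c).

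**It is a modelling choice.** Fitting the cohort and reading out one stratum is legitimate if the effect is the same in both. That is true, but the SAP does not state the assumption.

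**The model is withdrawn.** SAP 1.2.4 probably means it is never run. This stands, and it is the main reason the point is minor.

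**The silence is general.** The early-termination bullet covers five endpoints and gives no cohort or threshold for any of them. This also stands. It reads as summary wording, not as a decision to change the HbA1c population.

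A reader might infer that no surviving HbA1c summary names a subgroup. The documents do not support that: the first bullet of 1.2.4 and SAP 5.7.1 do, and so does Table 4, for Arm 2 only and by baseline HbA1c.

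**Conclusion.** The inconsistency is real and minor. SAP 5.7.1.2 sets the HbA1c co-primary in all Cohort A FAS patients, against SAP 5.7.1 and 10.1 and Protocol 3.2.3, 4.1 and 11.4.3.1. Its >7.0% week-12 difference is algebraically the common Cohort A effect. The practical gap is narrow: the between-arm week-12 HbA1c summaries in 5.7.1.2 and in the early-termination bullet of 1.2.4 do not repeat the >7.0% limit.

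A reader might go further and conclude that the co-primary estimate is biased, or that it will be reported in the wrong population. Neither follows. Bias requires effects that differ by stratum, and the documents give no effect at ≤7.0%. With effects there from equal to zero and a 78% share, the shift runs from 0 to 0.22, at most about a quarter of a standard error, and no formal hypothesis testing is planned. The model is probably not run, and 5.7.1 still gives the correct subgroup.

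The figures rest on the planned 10 per arm, SD 1.81, the planned effect applying at >7.0%, and balance within strata. The number enrolled at early termination is not given, so they describe the design and not the data in hand.

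**What to change.** 1. In SAP 5.7.1.2, and by reference in the early-termination bullet of 1.2.4, present the Cohort A week-12 HbA1c summaries and plots for FAS patients with screening HbA1c >7.0% as the co-primary display. An all-patient version is optional. Use screening HbA1c, as 1.2.4 requires, and not the baseline wording of Table 4.
2. Mark the HbA1c MMRM as not performed, in line with 1.2.4. If it is kept, either restrict it to screening HbA1c >7.0% and drop the constant stratum terms, or keep all of Cohort A and add treatment-by-stratum and treatment-by-stratum-by-time terms.

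The cost is SAP wording, fewer patients in the display and a wider interval where one is computed. At the planned size the 90% half-width would be 1.59 to 1.72 (restricted) or 1.58 to 1.69 (interaction terms), about 1.58 to 1.72 overall, instead of 1.40 for all of Cohort A.

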## 5.7.2. Analysis of Secondary Efficacy Variables

Statistical analyses for the secondary efficacy endpoints (defined in Section 4.7.2) and SBTP-specific secondary efficacy endpoints (described in Section 4.7.3) will be performed in the FAS population.

All measurements, scheduled or unscheduled, will be assigned to efficacy analysis windows defined in Appendix 10.2 in order to provide an assessment for these time points. For fasting TG, measurements on not-fasting patients will be excluded; the median percent changes (with Q1 and Q3 bars) will be plotted across visits by treatment group.

Multiple types of measurements are planned to be analyzed during differing time points in the trial, specifically continuous measurements expected to have a normal distribution (example: absolute change in HbA1c) and continuous measurements expected to have a non-normal distribution (example: TG).

The following patient groups are also used for analyzing secondary efficacy variables:

- Combined Cohort A+B include all patients in Cohort A and Cohort B as defined in Section 2.1.
- DBTP-stable patient is defined as a patient who meets both of the following two stability criteria:
  - Absolute change in HbA1c from baseline to week  $12 \le 0.5\%$
  - Percent change in fasting serum TG from baseline to week  $12 \le 25\%$

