9.2.4. Laboratory Testing

Detailed instructions for sample collection, along with the location for analysis, are in the laboratory manual provided to study sites.

Samples for laboratory testing will be collected at visits according to Table 1 and Table 2. On study visit days during which study drug will be administered, the laboratory samples are to be collected before the dose of study drug unless otherwise stated.

Fasting is only required for laboratory tests described as "fasting" (eg, fasting TG, fasting lipid panel, and fasting glucose).

Blood Chemistry

Sodium Total protein, serum Total bilirubin
Potassium Creatinine Uric acid

Chloride Blood urea nitrogen (BUN) Creatine phosphokinase (CPK)

Carbon dioxide Aspartate aminotransferase (AST) Gamma-glutamyl transferase (GGT)

Calcium Alanine aminotransferase (ALT) Gamma-glutamyl transferase (GGT)

Fasting Glucose Alkaline phosphatase

Albumin Lactate dehydrogenase (LDH)

Hematology

Hemoglobin Differential:
Hematocrit Neutrophils
Red blood cells (RBCs) Lymphocytes

White blood cells (WBCs)

Red cell indices

Platelet count

Monocytes

Basophils

Eosinophils

Urinalysis

Color Glucose
Clarity Blood
pH Bilirubin

Specific gravity Leukocyte esterase

Ketones Nitrite
Protein WBC

Fasting Lipid Panel

LDL-C Apolipoprotein B HDL-C Triglycerides

Total Cholesterol

Other Laboratory Tests

Fasting Leptin Pregnancy test (serum/urine) Fasting Free Fatty Acids

Hepatitis B surface antigen (sAg) HIV (Ab) HbA1c

Fasting Apolipoprotein C3 Fructosamine Hepatitis C (Ab)

Fasting ANGPTL3 Urine albumin and creatinine

Abnormal Laboratory Values and Laboratory Adverse Events

All laboratory values must be reviewed by the investigator or authorized designee.

Significantly abnormal test results that occur after start of treatment must be repeated to confirm the nature and degree of the abnormality. When necessary, appropriate ancillary investigations should be initiated. If the abnormality fails to resolve or cannot be explained by events or conditions unrelated to the study medication or its administration, the Medical/Study Director must be consulted.

The clinical significance of an abnormal test value, within the context of the disease under study, must be determined by the investigator.

Criteria for reporting laboratory values as an AE are provided in Section 10.1.1.

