## 4.7.2. Secondary Efficacy Variables

The secondary endpoints include:

- Percent change in fasting serum TG from baseline to week 24.
- Absolute change in HbA1c from baseline to week 24.
- Change in fasting glucose from baseline to week 12.
- Change in fasting glucose from baseline to week 24.
- Percent change in liver fat (MRI-PDFF) from baseline to week 12.
- Percent change in liver fat (MRI-PDFF) from baseline to week 24.
- Change on the daily lipodystrophy hunger questionnaire from baseline to week 12.
- Change on the daily lipodystrophy hunger questionnaire from baseline to week 24.

Regeneron Pharmaceuticals, Inc.

Page 24 of 88

Protocol: R4461-PLD-20100

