# 5.7. Analyses of Efficacy Variables

For statistics where international and conventional units do not impact the results (eg, means and least square (LS) means for percent changes from baseline, statistical testing for both percent and absolute changes from baseline, rates of patients below a threshold), derivations will be calculated and statistical models will be run using conventional units. For other statistics (eg, descriptive statistics at baseline and over time, absolute changes from baseline), derivations will be presented in both international and conventional units.

All efficacy assessment values obtained during the study (scheduled or unscheduled) can be used to provide a value for the efficacy endpoints as appropriate.

All efficacy measurements will be assigned to Efficacy Analysis Windows defined in Appendix 10.2, with the intent to provide an assessment for week 1 to 24 time points. For all visits post-baseline, the value used for the analyses at a given time point (eg, at week 12) is the value obtained within the corresponding efficacy analysis window. If multiple values exist for an analysis window, the value obtained closest to the targeted time of the window will be used as appropriate. Unless otherwise specified, the baseline value is defined as the last available measurement before the first double-blind study treatment administration. For patients randomized and not treated, the baseline value is defined as the last available value prior to the date of randomization.

Statistical analyses for the primary efficacy endpoints will be completed during the first step efficacy analysis (Section 7). Remaining descriptive efficacy analyses will be completed during the second step analyses.

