#### General common rules

All safety analyses will be performed, unless otherwise specified, using the following common rules:

- Safety data in patients who do not belong to the safety analysis sets (ie, exposed but not randomized) will be listed separately.
- Potentially Clinically Significant Values (PCSVs) or Potentially Clinically Significant Abnormalities (PCSAs) are defined as abnormal values considered medically important by the Sponsor according to predefined criteria/thresholds based on literature review and defined by the Sponsor for clinical laboratory tests, vital signs, ECG (PCSV version dated January 2009 [Appendix 10.4]).

Regeneron Pharmaceuticals, Inc.

Page 42 of 88

Protocol: R4461-PLD-20100

• PCSV criteria will determine which patients had at least 1 PCSV during the respective TEAE period, taking into account all evaluations including unscheduled or repeated evaluations.

Protocol: R4461-PLD-20100

Date: May 16, 2024

- The treatment-emergent PCSV denominator for a given parameter will be based on the number of patients assessed for that given parameter at least once during the respective TEAE period.
- All measurements, scheduled or unscheduled, fasting or not fasting, will be assigned
  to the Global Analysis Windows defined in Appendix 10.2 to provide an assessment
  for the screening visit through follow-up visit time points.
- For quantitative safety parameters including central laboratory measurements and vital sign scores, descriptive statistics will be used to summarize observed values and change from baseline values by visit.
- Unless otherwise specified, in the case of multiple assessments within an analysis
  window, the assessment closest to the protocol planned visit study day will be used in
  analysis.

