**Table 10: Analysis Windows for Body Weight** 

Visit Label	Targeted DBTP Study Day	Targeted SBTP Study Day	Analysis Window in Study Days	SBTP Analysis Window in Study Days
Screening	< Day 1	N/A	Measurement obtained prior to 1st study trt, and not defined as baseline visit	N/A
Baseline	Day 1	N/A	Measurement obtained closest to 1st study trt	N/A
Week 1	8	N/A	Day 2 to 15	N/A
Week 3	22	N/A	16 to 29	N/A
Week 5	36	N/A	30 to 39	N/A
Week 6	43	N/A	40 to 50	N/A
Week 8	57	N/A	51 to 64	N/A
Week 10	71	N/A	65 to 78	N/A
Week 12	85	N/A	82 to SB Day 1	N/A
Week 14	N/A	SB Day 15	N/A	SB Day 2 to 22
Week 16	N/A	29	N/A	23 to 36
Week 18	N/A	43	N/A	37 to 50
Week 20	N/A	57	N/A	51 to 64
Week 22	N/A	71	N/A	65 to 78
Week 24	N/A	85	N/A	79 to 92
FU- W5	Last study trt admin day + 35 days	Last study trt	Last study trt admin day +15 days TO last study trt admin day + 49 days	
FU-W9	Last study trt admin day + 63 days	Last study trt admin day + 50 days TO last study trt admin day + 77 days		
FU-W13	Last study trt admin day + 91 days	Last study trt admin day + 78 days TO last study trt admin day + 105 days		
FU-W17	Last study trt admin day + 119 days	Last study trt admin day + 106 days TO last study trt admin day + 126 days		

Table 11: Efficacy Analysis Windows for Fasting Triglycerides and Fasting Glucose

Visit Label	Targeted DBTP Study Day	Targeted SBTP Study Day	Analysis Window in Study Days	SBTP Analysis Window in Study Days
Screenin g	< Day 1	N/A	Measurement obtained prior to 1st study trt, and not defined as baseline visit	N/A
Baseline	Day 1	N/A	Measurement obtained closest to 1st study trt while remaining prior to 1st study trt admin	N/A
Week 2	15	N/A	Day 2 to 22	N/A
Week 4	29	N/A	23 to 36	N/A
Week 6	43	N/A	37 to 50	N/A
Week 8	57	N/A	51 to 64	N/A
Week 10	71	N/A	65 to 74	N/A
Week 11	78	N/A	75 to 81	N/A
Week 12	85	N/A	82 to SB Day 1	N/A
Week 14	N/A	SB Day 15	N/A	SB Day 2 to 22
Week 16	N/A	29	N/A	23 to 36
Week 18	N/A	43	N/A	37 to 50
Week 20	N/A	57	N/A	51 to 64
Week 22	N/A	71	N/A	65 to 74
Week 23	N/A	78	N/A	75 to 81
Week 24	N/A	85	N/A	82 to 92
FU- W5	Last study trt admin day + 35 days		Last study trt admin day +15 days TO last study trt admir day + 49 days	
FU- W9	Last study trt admin day + 63 days		Last study trt admin day + 50 d day + 77	
FU- W13	Last study trt admin day + 91 days		Last study trt admin day + 78 d day + 105	
FU- W17	Last study trt admin day + 119 days		Last study trt admin day + 106 days TO last study trt admin day + 126 days	

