### 10.4. Criteria for Potentially Clinically Significant Values (PCSV)

Table 20: Criteria for Potentially Clinically Significant Values (PCSV)

Parameter	PCSV	Comments
Clinical chemistry	y	
ALT	By distribution analysis:	
	>2 ULN and baseline ≤ 2 ULN	
	>3 ULN and baseline ≤ 3 ULN	
	>5 ULN and baseline ≤ 5 ULN	
	>10 ULN and baseline ≤ 10 ULN	
	>20 ULN and baseline ≤ 20 ULN	
AST	By distribution analysis:	
	>2 ULN and baseline ≤ 2 ULN	
	>3 ULN and baseline ≤ 3 ULN	
	>5 ULN and baseline ≤ 5 ULN	
	>10 ULN and baseline ≤ 10 ULN	
	>20 ULN and baseline ≤ 20 ULN	
Alkaline Phosphatase	> 1.5 ULN and baseline ≤ 1.5 ULN	
Total Bilirubin	> 1.5 ULN and baseline ≤ 1.5 ULN	
	> 2 ULN and baseline ≤ 2 ULN	
ALT and Total Bilirubin	ALT > 3 ULN and Total Bilirubin > 2 ULN and baseline ALT≤3 ULN or Total bilirubin ≤ 2 ULN	

Protocol: R4461-PLD-20100

Parameter	PCSV	Comments
СРК	> 3 ULN and ≤ 5 ULN and baseline ≤ 3ULN > 5 ULN and ≤ 10 ULN and baseline ≤ 5	
	ULN >10 ULN and baseline ≤ 10 ULN	
Creatinine	≥ 30% increase from baseline ≥ 60% increase from baseline	
Creatinine Clearance	≥15 - <30 (severe decrease in GFR) ≥30 - <60 (moderate decrease in GFR) ≥60 - <90 (mild decrease in GFR)	
Uric Acid Hyperuricemia	>408 μmol/L	
Blood Urea Nitrogen	≥17 mmol/L	
Chloride Hypochloremia: Hyperchloremia:	<80 mmol/L >115 mmol/L	
Sodium	$\leq$ 129 mmol/L $\geq$ 150 mmol/L	Must also be outside the normal range.
Potassium	< 3 mmol/L ≥ 5.5 mmol/L	Must also be outside the normal range.
Total Cholesterol	≥6.20 mmol/L (Under 18 yrs) >7.74 mmol/L (18 yrs +)	Must also be outside the normal range.
Triglycerides	<pre></pre>	Must also be outside the normal range.
Glucose	Hypoglycemia <3.9 mmol/L or 70 mg/dL  Hyperglycemia Fasting glucose ≥250 mg/dL or 13.9mmol/L and Increase in fasting glucose >50 mg/dL or 2.8mmol/L above baseline	Must also be outside the normal range.

Parameter	PCSV	Comments
		Comments
HbA1c	HbA1c ≥10.5% AND increase in HbA1c of ≥1.5% from baseline value	
Albumin	≤25 g/L	
Hematology		
WBC	< 3.0 Giga/L (3000/mm3)	Must also be outside the normal
	≥ 16.0 Giga/L (18 yrs +)	range.
Lymphocytes	>4.0 Giga/L	
	<0.6 Giga/L	
Neutrophils	< 1.5 Giga/L (1,500/mm3)	Must also be outside the normal range.
Eosinophils	> 0.5 Giga/L (500/ mm 3 )	
Losmopinis	or > ULN if ULN ≥ 0.5 Giga/L	
Monocytes	>1.5 Giga/L	
Hemoglobin	≤115 g/L (Male 18 yrs +)	Must also be outside the normal
	≤95 g/L (Female 18 yrs +)	range.
	≥185 g/L (Male 18 yrs +) ≥165 g/L (Female 18 yrs +)	

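### The SAP drops not-fasting samples for triglycerides but not for fasting glucose, and its safety rules conflict with the fasting wording of the high-glucose PCSV

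*SAP*

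**What the plan says.** **Efficacy.** Fasting glucose is a secondary endpoint in SAP 4.7.2 ("Change in fasting glucose from baseline to week 12", and likewise to week 24). SAP 4.7.3 adds the change from week 12 to week 24. It shares Table 11 in SAP 10.2 with triglycerides ("Efficacy Analysis Windows for Fasting Triglycerides and Fasting Glucose"), and that table sets no fasting condition. SAP 5.7 is permissive about which values may be used: "All efficacy assessment values obtained during the study (scheduled or unscheduled) can be used to provide a value for the efficacy endpoints as appropriate". SAP 6.5 lets unscheduled values supply a time point, baseline included.

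Not-fasting samples are excluded in two places. In 5.7.1.1, on the primary triglyceride analysis: "Measurements on not-fasting patients will be excluded". In 5.7.2, on secondary analyses: "For fasting TG, measurements on not-fasting patients will be excluded". Neither covers glucose.

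**Safety.** The common rules in SAP 5.8 read "All measurements, scheduled or unscheduled, fasting or not fasting, will be assigned" to the global windows, and they count every evaluation, unscheduled and repeat ones included, when deciding whether a patient had a PCSV. The high-glucose PCSV in SAP 10.4, Table 20, reads "Fasting glucose ≥250 mg/dL or 13.9mmol/L and Increase in fasting glucose >50 mg/dL" above baseline.

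**Collection.** Protocol 9.2.2.1 and 9.2.2.2 ask for a fast of about 12 hours for triglycerides and for glucose, in the same terms. Both allow a shorter fast where a contraindication is documented.

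**The concern.** The same tube of blood is treated in two ways. If a patient arrives unfasted, the SAP removes the triglyceride value and has no rule that removes the glucose value, although both endpoints carry the word fasting and both have the same collection rule. A meal before the week 12 draw would look like worse glycaemic control. A meal before the baseline draw would look like later improvement.

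In the safety tables, a programmer who follows the 5.8 rules would test every glucose value against the PCSV, while one who follows Table 20 would test fasting values only. The two tables could give different patient counts. The laboratory-derived fasting-glucose limb of the hyperglycemia AESI (SAP 4.8.1.2 and Table 19) raises the same question.

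**Working it through.** No stated figure depends on this point, so the check is mainly a comparison of text.

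**1. Rules side by side.**

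| | Triglycerides | Fasting glucose |
|---|---|---|
| Fast at collection | about 12 h (Protocol 9.2.2.1) | about 12 h (Protocol 9.2.2.2) |
| Scheduled days in TP1 and TP2 (Protocol Table 2) | 1, 15, 29, 43, 57, 71, 78, 85, 99, 113, 127, 141, 155, 162, 169 | the same |
| Analysis windows | SAP Table 11 | SAP Table 11 |
| Unscheduled values usable | yes | yes |
| Not-fasting values excluded from analysis | yes (SAP 5.7.1.1, 5.7.2) | no rule |

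Only the last row differs.

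**2. Routes into the endpoint.** The week 12 window runs from Day 82 to single-blind (SB) Day 1, and the week 24 window covers SB Days 82 to 92. A not-fasting glucose value reaches them if the scheduled draw was unfasted, or if an unscheduled value lies closest to target. Baseline is the last value before the first double-blind dose, so an unfasted Day 1 draw would become baseline.

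**3. Chemistry draws without a fasting-glucose visit.** Blood Chemistry is scheduled without Fasting Glucose on Days 8, 22, 92, 106 and 120. With SB day = study day − 84, the last three are SB Days 8, 22 and 36. In Table 11:
- Days 8 and 22 fall in week 2 (Days 2 to 22). Each is 7 days from target Day 15.
- SB Days 8 and 22 fall in week 14 (SB Days 2 to 22).
- SB Day 36 falls in week 16 (SB Days 23 to 36).

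None reaches week 12 or week 24. Each would be chosen only if the on-target sample were missing or further from target.

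**4. Scale of the effect on a mean (assumed values).** If k of n patients in an arm have a value raised by Δ at one time point, the arm mean moves by k × Δ / n. Take n = 10, the planned arm size within a cohort (Protocol 6.1.1):

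| | Δ = 20 mg/dL | Δ = 50 mg/dL | Δ = 100 mg/dL |
|---|---|---|---|
| k = 1 | 2 | 5 | 10 |
| k = 3 | 6 | 15 | 30 |

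The shift is upward if the affected value is post-baseline and downward in the change score if it is the baseline. Smaller arms move more: with n = 5, one value raised by 50 moves the mean by 50/5 = 10 mg/dL.

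**5. The PCSV needs both conditions.** Let F be the true fasting value and B a fasting baseline. An unfasted reading of F + Δ is flagged if F + Δ ≥ 250 and F + Δ − B > 50:
- Δ = 20: F ≥ 230 and a true rise above 30.
- Δ = 50: F ≥ 200 and any true rise above 0.
- Δ = 100: F ≥ 150, even if the true value had fallen by anything less than 50.

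A meal alone can therefore trigger the flag, but only in patients whose fasting glucose is already fairly high.

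**The case against.** **Fasting is already required.** The protocol requires it for glucose, the endpoint is named fasting glucose, and SAP 5.7 admits values only as appropriate. An unfasted sample departs from the protocol. This stands to the extent that the text leaves a gap and does not plan to use such values. It does not close the gap: the same requirement covers triglycerides, and the SAP still wrote an analysis exclusion for them.

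**Table 20 overrides the common rules.** The 5.8 rules apply unless otherwise specified, the fasting-or-not wording concerns assignment to windows, and Table 20 says fasting glucose. That is a fair reading and probably the intended one. But SAP 4.8.2 uses fasting glucose as the name of the chemistry analyte, so the label alone is not a filter, and the PCSV rule counts all evaluations without a fasting condition. A clarifying sentence is still needed.

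**Stronger readings the documents do not support.**
- A reader might infer that the chemistry draws on Days 8, 22, 92, 106 and 120 are non-fasting, because that row of the schedule has no fasting footnote. Protocol 9.2.4 says "Fasting is only required for laboratory tests described as" fasting, gives fasting glucose as an example, and lists the chemistry analyte as fasting glucose; SAP 4.8.2 does the same. At most, the missing footnote should be reconciled with 9.2.4. These days also never reach the week 12 or week 24 windows.
- A reader might extend the point to new-onset diabetes. Its glucose limb already requires two values after a fast of at least 8 hours.
- The low-glucose criteria carry no fasting condition and are not affected.

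**Conclusion.** The point holds as an omission on the efficacy side and an internal conflict on the safety side. As written, glucose from an unfasted scheduled or unscheduled draw can enter the fasting-glucose endpoint at baseline, week 12 or week 24, and the 5.8 rules disagree with the fasting wording of the high-glucose PCSV.

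The impact is modest. The endpoint is secondary and no formal hypothesis is tested (Protocol 11.1). After early termination, SAP 1.2.4 limits efficacy to descriptive summaries and plots. Those outputs still include fasting glucose, with few patients behind each mean, and the PCSV and AESI tables are not covered by that reduction.

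The size of any bias cannot be computed from the documents. The mg/dL shifts shown rest on assumed meal effects of 20 to 100 mg/dL and assumed counts of unfasted draws.

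**What to change.** **SAP 5.7.2.** Extend the triglyceride exclusion to fasting glucose, for baseline as well as post-baseline values. Apply it before the closest-to-target rule, so that another fasting value in the window can be used. Accept documented shortened fasts as fasting, and state how samples of unknown fasting status are handled.

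**SAP 5.8.** State that the high-glucose PCSV and the laboratory-derived fasting-glucose limb of the hyperglycemia AESI use fasting values only. State that new-onset diabetes keeps its own condition of at least 8 hours, which a 12-hour flag must not override. State that the low-glucose criteria use all values. While there, reconcile the hyperglycemia AESI in 4.8.1.2, which includes symptoms, with Table 19, which omits them.

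**Schedule.** Reconcile the Blood Chemistry row with Protocol 9.2.4 on fasting.

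**Cost.** A sentence or two in each SAP section, and a few glucose values that become missing. The triglyceride exclusion already presupposes that fasting status can be identified for the draw, so no new data item should be needed.
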